645 estradiol and progesterone (women only). Urine pregnancy test (β -hcg) will be done in females only.
646 The DXA scan will not be performed if the pregnancy test is positive.

647 **Blood Withdrawal**

648 Blood withdrawal will remain within the NIH guideline of <10.5 mL/kg or <550 mL (whichever
649 is smaller) every 8 weeks for research purposes. The total amount of blood drawn is detailed below.

650

651

Tests	Amount
Screening lab work	32 mL
OGTT	151 mL
Fasting blood measurements	
EBL chamber (pre- and post-)	76 mL
CIT chamber (pre- and post-)	60 mL
FST chamber (pre- and post-)	60 mL
Total (baseline admission):	379 mL
Outpatient visits	
6 months	32 mL
1 year	32 mL
Total:	443 mL

652

653 **Sample Size Calculation**

654 The sample size calculation to answer the primary research question is based on the number
655 of patients needed to demonstrate an association between any change in EE due to interventions and
656 subsequent change in energy intake. In preliminary analyses using data from our clinical research unit
657 [13], the cross-sectional Pearson correlation between unadjusted 24-h EE during energy balance and
658 energy intake is 0.46 ($p<0.0001$). A target sample size of 46 participants will provide a power of
659 greater than 0.80 with an alpha of 0.05 to detect a 0.40 correlation ($r^2=0.16$) using simple linear
660 regression assuming that the association between change in EE and change in energy intake will be
661 the same as that between EE and energy intake. However, any finding will subsequently be adjusted
662 in multivariate linear regression analysis for age, sex, race, fat mass and fat free mass (5 covariates),
663 which requires a minimum of 50 volunteers. In addition, given the number of analyses that will be
664 done, an alpha of 0.01 is likely more appropriate. Therefore, to detect a correlation of 0.4 with a
665 power >0.80 at an alpha = 0.01, a total of 68 subjects will be enrolled for the core study (Table 2).

666

667 **Table 2. Sample size calculations achieving a statistical power ≥ 0.8 .**

	$\alpha=0.05$	$\alpha=0.01$	$\alpha=0.005$	$\alpha=0.001$
r=0.50	n=29	n=41	n=47	n=59
r=0.40	n=46	n=68*	n=77	n=98
r=0.30	n=84	n=124	n=142	n=181

668 r: Pearson's unadjusted correlation between change in EE and change in energy intake

669 α : significance level (2-sided)

670 *: Sample size for the final analysis

671

672 An interim analysis will be conducted when a target sample size of 47 subjects complete the

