673 baseline admission. This sample size will provide 80% power ($\alpha=0.005$) to detect a simple

674 correlation of 0.5 between change in EE due to any intervention and change in energy intake. The

675 alpha level for this interim analysis is set to 0.005 based on the alpha spending function approach

676 [[64, 65]]. The alpha level for the final analysis will remain at 0.01. More importantly, the interim

677 analysis will allow us to assess whether there is likely to be a significant correlation once the full

678 sample size is reached or whether the null hypothesis is highly likely to be accepted. If the correlation

679 within the first 47 subjects is <0.2 , the study will be stopped as the null hypothesis will be highly likely

680 to be accepted. However, if the correlation is much stronger than anticipated, the study will continue

681 to obtain adequate sample size for adjusting for covariates and answering the secondary research

682 questions. If the interim correlation is between 0.2 and 0.4, the final sample size will be increased

683 from 68 to 124 subjects to provide 80% power at an alpha of 0.01 to detect a more moderate

684 association. Achieved power as a function of final sample size, alpha and correlation value between

685 change in EE and energy intake is reported in Table 3. Assuming a 30% dropout rate, we will ask for a

686 total enrollment of 160 subjects.

687

688 **Table 3. Power calculations based on different values of alpha (α), correlation value (r) and**
 689 **sample size (n).**

α	r	n	Power
0.001	0.30	47	0.103
		68	0.208
		124	0.544
	0.40	47	0.308
		68	0.547
		124	0.915
	0.50	47	0.635
		68	0.873
		124	0.997
0.005	0.30	47	0.223
		68	0.378
		124	0.727
	0.40	47	0.503
		68	0.732
		124	0.969
	0.50	47	0.803*
		68	0.949
		124	0.999
0.01	0.30	47	0.301
		68	0.470
		124	0.799
	0.40	47	0.598
		68	0.804**
		124	0.982
	0.50	47	0.863
		68	0.969
		124	1.000

690 *: interim analysis

691 **: final analysis

692
 693 **Data Analysis**

694 Our primary outcome will be the association between the change in EE and the change in
 695 energy intake induced by the interventions (cool temperature exposure and fasting). As the purpose
 696 of this protocol is to evaluate the effects of altered EE on food intake regardless of the type of
 697 intervention, only within-subject analyses rather than between-interventions analyses will be carried

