771 evaluated and compared by the BIC statistic to identify the best model for weight data over time.
772 Changes in EE after 24-h of fasting and its association with changes in body weight at 6 months and 1
773 year will be combined with data from prior studies (using the exact same methodology) to increase
774 the statistical power of the weight change analysis (currently we have >60 subjects with complete
775 data available at baseline).

776 Statistical analysis will be performed using SAS with E-guide (SAS Institute, Cary, NC). All tests
777 of primary outcome measures will have a 2-sided Type 1 error of $p=0.01$. For the secondary outcome
778 analyses, we will control for Type 1 error at the level of the comparison with $p=0.05$ as each
779 hypothesis is substantively important and stated *a priori*.

780 **Informed Consent Process**

781 Written informed consent will be obtained from the participant prior to any screening visits,
782 study procedures or treatments. The person obtaining consent will explain the study in language
783 understandable to the subject. Sufficient time and opportunity will be given for discussion of the
784 research as well as to answer any questions they may have, taking care to minimize or eliminate the
785 perception of coercion or undue influence. The participant and the investigator will sign the current
786 IRB-approved informed consent document. A copy of the consent will be given to the subject for
787 future reference. The signed documents will be sent to the Medical Records Department for
788 placement in the subject's permanent record.

789 Participants will have the opportunity to carefully review the written consent form, either as a
790 physical or electronic document, and ask questions prior to signing. Participants will be informed that
791 participation is voluntary and that they may withdraw from the study at any time, without prejudice.

792 The consenting process may be performed using the NIH iMedConsent platform (which is 21
793 CFR Part 11 compliant). If the iMedConsent platform is used, then the participant and consenting
794 investigator will review and sign the current IRB-approved electronic informed consent document
795 using a hand signature (e.g., signing using a finger, stylus, or mouse). Electronic signatures (i.e., the
796 “signature” and a timestamp are digitally generated) will not be used. If a paper copy of the IRB-

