936 treated with the same protection and confidentiality as all other medical records. If requested by an
937 insurance company and the subject has signed a release of information, data from the study may be
938 made available to insurance companies. This could theoretically affect future insurability and
939 employment opportunities. These facts will be emphasized during the consent process.

940

941 **Clinical Monitoring**

942 Study procedures will be subject to audits and/or monitoring visits to ensure compliance with
943 the protocol and applicable regulatory requirements consistent with the NIDDK quality assurance
944 program plan. Audit and/or monitoring visits results will be reported to the Principal Investigator for
945 further reporting as appropriate. Study documents and hospital records will be reviewed to verify
946 that the conduct of the study is consistent with the protocol plan.

947

948 **Data and Safety Monitoring**

949 Since this is not a medical intervention trial, the principal investigator will act as the data and
950 safety monitor. Data collection is the responsibility of the clinical trial staff at the site under the
951 supervision of the site manager. The investigator is responsible for ensuring the accuracy,
952 completeness, legibility, and timeliness of the data reported. The PI and study team will review
953 participant data on a monthly basis to review the data for safety and efficacy. Events meeting
954 requirements for expedited reporting as described in HRPP Policy 801 will be submitted within the
955 required timelines.

956

957 **Event Reporting**

958 Adverse events, non-compliance both serious or continuing, protocol deviations both major and
959 minor, as well as unanticipated problems are defined & described by the NIH Office of Human
960 Subjects Research Protection policy #801, and will be reported in accordance with this policy.

961

962 **Research Use and Disposition of Human Samples and Data and Data Sharing**

963 Blood (stored as plasma or serum) and urine samples not immediately used for study purposes will be
964 stored for future measurements. All samples will be initially stored in freezers located on the
965 premises at the NIH in Phoenix, AZ. Stored samples and specimens will be used only to measure
966 factors that relate to diabetes, obesity, and their complications. All stored samples, specimens, and

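### The interim test at 0.005 followed by an unreduced final test at 0.01 is not alpha spending, so the two-sided 0.01 for the primary outcome is not assured

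*Combined protocol and SAP*

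**What the plan says.** All of the following is in the combined protocol and SAP.

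- **Sample Size Calculation, timing.** "An interim analysis will be conducted when a target sample size of 47 subjects complete the" baseline admission.
- **Sample Size Calculation, interim level and power.** The "alpha level for this interim analysis is set to 0.005 based on the alpha spending function approach". The look has 80% power for a "correlation of 0.5 between change in EE due to any intervention and change in energy intake". Table 3 marks the corresponding 0.803 as the interim analysis.
- **Sample Size Calculation, final level.** "The alpha level for the final analysis will remain at 0.01". The planned final size is 68, for r=0.4 with power above 0.80 at 0.01.
- **Sample Size Calculation, interim actions.** An interim correlation below 0.2 stops the study. One between 0.2 and 0.4 raises the final size from 68 to 124, again at 0.01. A much stronger correlation changes nothing: "to be accepted. However, if the correlation is much stronger than anticipated, the study will continue".
- **Data Analysis, closing paragraph.** All tests "of primary outcome measures will have a 2-sided Type 1 error of" 0.01.
- **Data and Safety Monitoring.** The principal investigator and study team look at "participant data on a monthly basis to review the data for safety and efficacy".

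The plan does not say whether p<0.005 at n=47 rejects the null hypothesis, which spending function is meant, or whether the 0.2 threshold applies to signed r or to |r|.

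**The concern.** Under alpha spending, error used at an interim look is no longer available at the end. Here 0.005 is assigned to the interim and the final test still receives the whole 0.01, so the named method and the stated levels contradict each other.

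The interim test is also not obviously inert. A level was chosen for it and its power was calculated, which invites a reader, or a later author, to treat crossing it as a positive result. Yet the plan attaches no action to crossing it. The actual type I error therefore depends on a question that the plan leaves open.

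This matters because the sponsor moved from 0.05 to 0.01 deliberately, in view of the number of analyses. A level chosen for that reason should be demonstrably controlled.

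A separate, smaller point is that a monthly review of efficacy by the study team sits uneasily beside a single planned look that can stop the study or nearly double it.

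**Working it through.** **Inputs.** Interim n=47 at 0.005; final n=68 or 124 at 0.01; stop if r<0.2; increase if r is 0.2 to 0.4 (Sample Size Calculation). Two-sided 0.01 for primary tests (Data Analysis). Assumed: bivariate normal data, one primary correlation, and a final analysis that includes the first 47 participants.

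**Step 1. Reproduce the stated powers.** With t the two-sided critical value on n−2 degrees of freedom, the critical correlation is r_c = t/√(n−2+t²). Power ≈ Φ{[atanh(r) + r/(2(n−1)) − atanh(r_c)]·√(n−3)}.

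- n=68, r=0.4, level 0.01: r_c=0.3104. The bracket is 0.4236+0.0030−0.3210=0.1056. Multiplied by √65 this is 0.851, so power is 0.803 (stated 0.804).
- n=47, r=0.5, level 0.005: r_c=0.4028, power 0.802 (stated 0.803).
- n=124, r=0.3, level 0.01: r_c=0.2305, power 0.798 (stated 0.799).

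The power calculations are sound. The issue is the combination of levels.

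**Step 2. Two looks, a claim possible at either.** Under no association the two test statistics are approximately bivariate normal with correlation √(47/68)=0.831. The error is 1 − P(|Z₁|≤2.807 and |Z₂|≤2.576) = 0.0125. Equivalently, 0.005 + 0.010 less an overlap of 0.0025. The simple sum of 0.015 overstates it because the looks share data.

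**Step 3. The full rule, simulated under zero correlation** (1 million or more trials, Monte Carlo standard error about 0.0001):

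| Reading of the plan | Two-sided error |
|---|---|
| Claim at 47 or 68, no futility stop or increase | 0.0125 to 0.0127 |
| Claim at either look, increase to 124, stop non-binding | 0.0115 to 0.0120 |
| Claim at either look, increase, binding stop on \|r\|<0.2 | 0.0110 to 0.0111 |
| Claim at either look, increase, binding stop on signed r<0.2, significant negative interim result counted | about 0.008 |
| As above, negative interim result not counted | about 0.0056 |
| Claim at the final only, n=68 | 0.0100 |
| Claim at the final only, increase to 124, stop non-binding | 0.0089 to 0.0094 |

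A positive interim result significant at 0.005 needs r above 0.403. That lies outside the 0.2 to 0.4 band, so such a trial stays on the n=68 path.

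**Step 4. Is 0.005 a recognisable spending value?** For a total of 0.01 at information 47/68=0.691, an O'Brien-Fleming-type function spends about 0.0019 and a Pocock-type function about 0.0078. At 47/124=0.379 a Pocock-type function spends about 0.0050, but the final level would then still have to fall.

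**Step 5. Final level that restores 0.01 if the interim may support a claim, ignoring futility.** At n=68 it is about 0.0071, with power 0.768 at r=0.4; 80% power then needs about 73 participants. If 124 were fixed in advance it is about 0.0057, with power 0.741 at r=0.3; 80% power then needs about 139.

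**The case against.** The strongest reply is that the interim is not an efficacy test at all. The plan has no efficacy stop, presents the futility and sample-size purpose as the more important one, and names 0.01 as the level for primary tests. If only the final test decides, 0.01 is held exactly at n=68 and with room to spare after the increase. A second reply is that the stop is worded as mandatory and, read literally, applies to signed r. Then the two-sided error is about 0.008 even if interim claims count.

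Both replies stand as far as they go. They rule out a stronger reading that a reader might infer, namely that the plan demonstrably breaks its 0.01. Exceeding it requires two things the text does not establish: that an interim p<0.005 counts as a rejection, and that the stop is non-binding or read on |r|. The figure of 0.008 is low largely because a signed stop removes most rejections in the negative direction. The upper tail is about 0.0056, against half of 0.01, but the plan sets no one-sided level, so that is not a breach.

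A reader might also infer that monthly efficacy review inflates the error further. The documents give no test, threshold or action for that review, so no error rate can be attached to it.

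What the replies do not answer is why a level attributed to alpha spending was set and powered if crossing it has no meaning, or how a spending scheme leaves the final level untouched.

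**Conclusion.** The stated levels do not form an alpha-spending scheme, and control at two-sided 0.01 depends on decisions the plan does not state. The excess is modest: at most about 0.0125 against 0.01 under the plan's own rules, and none if the interim makes no claim or the signed stop is binding. This is an unclear decision rule rather than an error in the power arithmetic, which reproduces. It should be corrected because the error statement is wrong as written and the correction is cheap.

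The figures assume a single primary correlation, bivariate normal data and cumulative data at the final analysis. The monthly review needs clarifying but is not evidence of inflation.

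**What to change.** **Preferred.** State that the look at n=47 makes no significance claim and serves only the futility and sample-size decisions. Delete the 0.005 level, its power statement and the alpha-spending reference. Keep 0.01 for the final test. This is wording only and costs no power.

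**If an interim claim is wanted.** Name the spending function and lower the final level to about 0.007 at n=68. Power at r=0.4 falls from 0.80 to about 0.77. Recompute the level for the path to 124, where the final size depends on the interim correlation; the 0.0057 above, for a size fixed in advance, is only a guide.

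**In either case.** Say whether the 0.2 threshold applies to signed r or |r|, and whether the stop is binding.

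**Separate clarification.** Reconcile the monthly review in Data and Safety Monitoring with the single planned look, by stating that the primary correlation is not computed outside the n=47 and final analyses.

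### The interim stop applies to any correlation below 0.2, so strong negative correlations that reject the two-sided null also stop the study on the ground that the null will be accepted

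*Combined protocol and SAP*

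**What the plan says.** All passages are in the combined protocol and SAP.

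- **Sidedness.** The Table 2 footnote defines alpha as "significance level (2-sided"). The end of Data Analysis says that all tests "of primary outcome measures will have a 2-sided Type 1 error of" 0.01.
- **Interim test.** Sample Size Calculation places the interim look at 47 completers of the baseline admission. The "alpha level for this interim analysis is set to 0.005", and then: "The alpha level for the final analysis will remain at 0.01".
- **Stop.** The study ends if the correlation "within the first 47 subjects is <0.2 , the study will be stopped as the null hypothesis will be highly likely" to be accepted.
- **Other zones.** An interim correlation between 0.2 and 0.4 raises the final sample from 68 to 124. One well above expectation means the study carries on. No zone mentions a negative value.
- **Scope.** Data Analysis defines the primary outcome as the association between change in EE and change in intake under both cold and fasting. It computes change in EE relative to energy balance. The interim power statement refers to change in EE from any of the interventions.
- **Expected direction.** Primary hypothesis 1 expects a positive association for cold. Secondary hypothesis 1 expects a larger fall in EE on fasting to go with more eating afterwards.

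**The concern.** A two-sided test treats r=-0.45 and r=+0.45 as equal evidence against the null. The interim rule, read as written, does not: the first stops the study and the second lets it continue. The reason given for stopping is that the null will probably stand. That suits values near zero, but not a correlation that has just rejected the null.

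The negative side is not remote. If change in EE is fasting EE minus energy-balance EE, a larger fall is a more negative number. Pairing larger falls with more intake then gives a negative r, so data supporting the sponsor's own fasting hypothesis could trigger the stop. At stake are power in that direction and a stop justified by a false statement.

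**Working it through.** **Inputs.** From Sample Size Calculation, Tables 2 and 3 and Data Analysis: interim n=47 at alpha 0.005; final n=68, or 124 if increased, at alpha 0.01; zone limits 0.2 and 0.4. Assumptions: bivariate normal data, one EE-intake pair driving the rule, and n=68 when the interim correlation is above 0.4.

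**1. Reproduce the plan's powers.** The Fisher approximation is power = Φ(atanh(r)·√(n-3) - z), with z the two-sided critical value.
- n=47, r=0.5, alpha 0.005: 0.549 × 6.633 - 2.807 = 0.837, giving 0.799. Simulating r gives 0.803; Table 3 states 0.803.
- n=68, r=0.4, alpha 0.01: 0.424 × 8.062 - 2.576 = 0.840, giving 0.799. Simulation gives 0.804; Table 3 states 0.804.
- One-sided tests would give 0.863 and 0.867, so the tables are two-sided.

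**2. Where rejection and stopping overlap.** Critical |r| = t/√(t² + n - 2). With 45 degrees of freedom and two-sided 0.005, t=2.952, so |r| = 2.952/√(8.71 + 45) = 0.403. Every r at or below -0.403 therefore rejects and is also below 0.2. For example, r=-0.45 has p=0.0015 and r=-0.50 has p=0.00035.

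**3. Is the stated reason true?** Conditional power at n=68 under the current trend is Φ((|atanh r|·√65 - 2.576)/√(21/65)), ignoring the opposite tail.
- r=+0.2 or -0.2: (1.634 - 2.576)/0.568 = -1.66, giving 0.05. The reason fits.
- r=-0.3: (2.495 - 2.576)/0.568 = -0.14, giving 0.44, or 0.85 if n were raised to 124. The reason does not fit. The interim p is 0.040, so this value does not reject at 0.005, but +0.3 would have led to 124 subjects.
- r=-0.4: (3.415 - 2.576)/0.568 = 1.48, giving 0.93. The reason is false.

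**4. Operating characteristics.** These come from simulating the whole rule. Rejection counts either the interim test at 0.005 or the final test at 0.01.

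| True r | Stop at 47, literal | Reject, literal | Reject, fixed n=68 | Stop at 47, \|r\| | Reject, \|r\| |
|---|---|---|---|---|---|
| -0.30 | 0.9996 | 0.22 | 0.47 | 0.23 | 0.68 |
| -0.40 | >0.9999 | 0.50 | 0.80 | 0.07 | 0.92 |
| 0 | 0.91 | 0.008 | 0.010 | 0.82 | 0.011 |
| +0.40 | 0.07 | 0.92 | 0.80 | 0.07 | 0.92 |

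At a true r of -0.50 the literal rule stops essentially every trial and rejects in 0.80 of them, all at the interim. Under no association the expected sample size is about 54 with the literal rule and 60 with |r|.

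**The case against.** The strongest reply is that magnitude was meant. The text never says that the correlation is signed. The stated reason is true for |r| and false for signed r, the neighbouring rules speak of strength, and Tables 2 and 3 use positive r as an effect size in two-sided calculations. This reading is plausible. But Data Analysis writes a detectable hormone correlation of -0.30 with its sign, so the authors do use signs, and a rule that ends a study should not rest on inference.

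A second reply is that stopping when the association points the wrong way may be deliberate: the cold hypothesis is positive and the motivating correlation is +0.46. That is a legitimate design, and for true r of +0.3 or more the two readings behave alike. The stated reason would still be wrong. On fasting, coding the fall in EE as a positive quantity makes the expected r positive. The plan does not fix this coding, and its definition of change relative to energy balance points to the signed form.

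A reader might infer several stronger things that the documents do not support.
- **No power, or no conclusion, in the negative direction.** The plan has its own interim test, which can reject at r of -0.403 or below. Only final-analysis power vanishes.
- **Table 3 is wrong.** Its entries are fixed-n powers and do not claim to model the stopping rule.
- **A negative result would be reported as no association.** No passage sets such a reporting rule.
- **Relabelling the test as one-sided costs nothing.** The interim 0.005 would also need converting (one-sided equivalent 0.0025), and the sidedness statement covers every primary test.

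**Conclusion.** The point holds on the written text: a two-sided test is paired with a stop that is open-ended on the negative side, and the reason given for that stop is false there. The contradiction is outright at r of -0.403 or below. For moderately negative r the reason is unsupported and the treatment is asymmetric.

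At a true r of -0.40, total power is about 0.50, compared with 0.80 for a fixed n=68 and about 0.92 with the rule on |r|. At -0.30 it is 0.22 compared with 0.68 on |r|. No figure in the documents says that the true r is this negative; these are illustrations at the mirror image of the plan's planning values. They rest on the three assumptions listed in the check. The literal rule does not inflate type 1 error; the null rejection rate is about 0.008. This should be corrected before the interim look.

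**What to change.** Write the interim rule on the absolute correlation: stop if |r| is below 0.2, and increase to 124 if |r| is 0.2 to 0.4. State for each intervention whether change in EE is a signed difference from energy balance or the size of the rise or fall, and name the correlation that drives the rule.

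This takes a sentence or two. Under no association, the stop probability falls from 0.91 to 0.82 and the expected sample size rises from about 54 to 60. The total null rejection rate over both looks rises from about 0.008 to 0.011, slightly above the stated 0.01, so the overall level should be checked when the rule is rewritten.

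If stopping for a negative association is intended, keep the rule, call it a one-directional futility rule, and give as its reason that a positive association is unlikely to be shown. The lower power on the negative side then remains and should be acknowledged.

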172 1. To investigate whether increases in 24-h EE by cold exposure lead to increased *ad libitum* food
173 intake, as measured using a vending machine paradigm.

174 2. To determine whether the effects of increased EE due to cool temperature exposure on
175 energy intake are only concomitant with the increase in EE or persist until the following day.
176 This will be explored by repeating the cool temperature exposure intervention twice: i) once
177 inside the whole-room calorimeter with an *ad libitum* diet; and, ii) once inside the whole-room
178 calorimeter during a fixed diet, followed by one day of *ad libitum* food intake on the vending
179 machines.

180 **Secondary Aims**

181 1. To determine whether 36 hrs of fasting will result in a change in energy intake on the following
182 day, and to determine whether the decrease in 24-h EE during fasting will correlate with
183 amount of food consumed the following day.

184 2. To determine if cold exposure will alter the 24-h respiratory quotient (RQ, an approximation
185 for the ratio of carbohydrate-to-fat oxidation rates), and test whether the induced RQ changes
186 independently contribute to the altered energy intake.

187 3. To determine if the 24-h EE responses to cool temperature exposure correlate with core body
188 temperature or changes in peripheral skin temperatures, and to determine if these changes
189 are related to body adiposity or associated with food intake.

190 4. To assess if behavioral testing addressing dietary restraint, stress related eating behaviors, and
191 executive function or the responses to visual analogue scales assessing hunger modify any
192 observed EE to energy intake association.

193 5. To assess whether the above behavioral testing as measured by previously validated

194 questionnaires and tasks are associated with measured food intake or hormone

195 concentrations.

196 6. To assess if concentrations of appetitive or exercise-induced hormones will correlate with the

197 observed changes in EE and energy intake.

198 7. To determine if any observed association between EE and energy intake predicts future weight

199 change at 6 months and 1 year.

200 **HYPOTHESES**

201 **Primary Hypotheses**

202 1. An increase in 24-h EE, as induced by 24 hours of exposure to 19°C, will be associated with an

203 increase in *ad libitum* food intake, which will exceed the increase in 24-h EE, on the day of the

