619 occur with *ad libitum* food consumption to wane. Subjects will be fed a weight maintaining diet.

620 **Day 21:** Subjects will spend approximately 23.25 hrs inside the respiratory chamber at 24°C but with
621 no food intake, for assessment of 24-h EE while fasting. Water will be provided and volunteers will be
622 encouraged to stay well-hydrated. Prior to entering the respiratory chamber, fasting blood will be
623 collected for measurement of plasma glucose and insulin. A 24-h urine collection will again be done
624 for nitrogen, cortisol and catecholamines. The CorTemp™ core body temperature monitoring system
625 will be used to assess changes in body temperature during fasting. Subjects will again be asked to
626 wear 9 iButtons® to measure skin temperature changes during fasting. Subjects will complete the
627 VAS at 3 time points during the 24 hours inside the calorimeter.

628 **Day 22:** Upon exiting the chamber, the subjects will complete the VAS. Fasting blood will be then
629 collected for measurement of insulin, glucagon, leptin, adiponectin, ghrelin, IGF-1, active GLP-1, PP,
630 PYY, IL-6, free T3, free T4, TSH, FGF21, estradiol and progesterone, beta-hydroxybutyrate, lactate,
631 pyruvate. Subjects will spend 24-h using the vending machine paradigm on the floor, as above. The
632 results of this vending machine assessment will be used to ascertain the amount of intake following a
633 maximal energy deficit, as a baseline comparison.

634 **Day 23:** Participants will complete the vending machine exit questionnaire, an 11-item questionnaire
635 designed by our staff to assess motivation to eat while using the vending machines. This *ad hoc*
636 questionnaire includes items related to mood, liking of food, and timing of meals. Subjects will then
637 be discharged home.

638 **Outpatient Visits**

639 Volunteers will be invited to return after 6 months and 1 year from the date of discharge. On
640 these visits, vital signs and weight data will be obtained. Volunteers will also have an assessment of
641 body composition by DXA and will be administered the IPAQ and FFQ questionnaires to have
642 measures of physical activity and dietary intake, respectively, during the follow-up period. Fasting

643 blood collection will be done for measurement of complete blood cell count, platelet count, glucose,
644 electrolytes, plasma urea nitrogen, creatinine, liver function tests, thyroid profile as well as plasma

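### Enrolling 160 with 30% dropout is expected to yield 112 analysed participants, not the 124 on which the expanded sample's 80% power rests

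*Combined protocol and SAP*

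**What the plan says.** All the figures are in the protocol's Sample Size Calculation section.

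- The core design: "a total of 68 subjects will be enrolled for the core study", sized for r = 0.40 at alpha 0.01.
- The interim look: "An interim analysis will be conducted when a target sample size of 47 subjects complete the" baseline admission, so it counts completers.
- The expansion: an interim correlation of 0.2 to 0.4 raises the final sample "from 68 to 124 subjects to provide 80% power at an alpha of 0.01 to detect a more moderate" association. Tables 2 and 3 tie 124 to r = 0.30.
- The power table: "Achieved power as a function of final sample size, alpha and correlation value between" change in EE and change in energy intake is given in Table 3, with 0.799 for n = 124, r = 0.30, alpha 0.01.
- The enrolment request: "Assuming a 30% dropout rate, we will ask for a" "total enrollment of 160 subjects".

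No inflation formula is printed, and the plan does not say which stage the 30% refers to.

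**The concern.** The expanded sample, the dropout rate and the enrolment figure appear together as the support for 80% power at r = 0.30. The 124 is a number analysed: Table 2 footnotes its starred n as the one for the final analysis, Table 3 is indexed by final sample size, and the interim counts people who finished the admission. If 124 instead meant people enrolled, there would be no reason to inflate it to 160.

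Read that way, 160 enrolled with 30% lost does not deliver 124. The expansion branch would be expected to run with fewer participants than its stated power requires. That branch matters because, if the true correlation is 0.30, it is the most likely result of the interim look.

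**Working it through.** **Inputs** (Sample Size Calculation; sidedness from the note to Table 2 and the end of Data Analysis): expanded n = 124; dropout 30%; enrolment 160; r = 0.30; two-sided alpha 0.01; core n = 68; interim n = 47.

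**1. The plan's own power figure.** An exact calculation for a Pearson correlation under bivariate normality reproduces all 27 entries of Table 3 to three decimals, including 0.799 for n = 124, r = 0.30, alpha 0.01. The Fisher z approximation can be checked by hand:

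power ≈ Φ(atanh(r) × √(n − 3) − 2.576), with atanh(0.30) = 0.3095

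- n = 124: 0.3095 × √121 − 2.576 = 3.405 − 2.576 = 0.829, so power ≈ 0.796 (exact 0.799).

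**2. The enrolment figure.**

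- Expected completers: 160 × (1 − 0.30) = 112.
- Enrolment for an expected 124: 124 / 0.70 = 177.1, so 178.
- Largest loss that leaves 124 of 160: 1 − 124/160 = 22.5%.
- Core design: 68 / 0.70 = 97.1, so 98 enrolled would suffice and 160 is ample.
- For comparison, 124 × 1.3 = 161.2, which is close to 160. This would fit adding 30% instead of dividing by 0.70, but the plan does not show how 160 was obtained.

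If each of 160 enrollees independently completes with probability 0.70, the chance of at least 124 completers is about 2%.

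**3. Fixed-n power at 112.**

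- Fisher z: 0.3095 × √109 − 2.576 = 3.231 − 2.576 = 0.656, so power ≈ 0.744. The exact value is 0.747.
- Correlation giving 80% power: tanh((2.576 + 0.842) / √109) = tanh(0.327) = 0.316. Other variants of the calculation give 0.315 to 0.316.
- At r = 0.40 the loss is about 1 point: 0.968 at 112 against 0.982 at 124.

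**4. Sensitivity to the loss that applies before the primary analysis** (160 enrolled, r = 0.30, alpha 0.01):

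| Loss | Analysed | Fixed-n power |
|---|---|---|
| 20% | 128 | 0.81 |
| 22.5% | 124 | 0.80 |
| 25% | 120 | 0.78 |
| 27.5% | 116 | 0.76 |
| 30% | 112 | 0.745 |

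**5. Power once expansion has been triggered.** In simulation with a true r of 0.30, the interim correlation at n = 47 is below 0.2 in 23.2% of trials, between 0.2 and 0.4 in 53.8%, and above 0.4 in 23.1%. Among trials in the middle band:

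| True r | Power, 112 analysed | Power, 124 analysed |
|---|---|---|
| 0.25 | 0.641 | 0.697 |
| 0.30 | 0.795 | 0.844 |
| 0.35 | 0.903 | 0.936 |

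These exceed the fixed-n values at r = 0.30 because trials with an interim correlation below 0.2 have been removed.

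**The case against.** The arithmetic is not in dispute. The case on the other side is about weight.

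- **The practical loss is modest.** The difference between 112 and 124 arises only after expansion, and there power at r = 0.30 is about 0.795 even with 112. Over the whole design (stop below 0.2, expand at 0.2 to 0.4, and, by assumption, stay at 68 above 0.4), power with 112 against 124 is about 0.644 against 0.671 at r = 0.30, 0.804 against 0.821 at 0.35, and 0.910 against 0.917 at 0.40. This stands and limits the point's importance. It does not reconcile the three printed numbers, and Table 3 is itself on the fixed-n basis.
- **The 160 is a request that can be amended.** Attrition among the first participants will be known at the interim, so enrolment could be raised then. That is possible, but a later amendment does not make the present figures agree.
- **Dropout may include follow-up loss.** "Volunteers will be invited to return after 6 months and 1 year from the date of discharge", and those visits serve a secondary aim: "To determine if any observed association between EE and energy intake predicts future weight" change. The primary correlation needs only inpatient data. If part of the 30% is follow-up loss, more than 112 would be analysed. This is a real alternative, but the plan neither says so nor gives an inpatient loss rate.
- **Withdrawn volunteers may be re-enrolled.** The withdrawal section allows this to be considered, while the Remuneration section says that people who leave the unit will generally not return, subject to case-by-case review. No rate is given, and it is not said whether a returner counts again toward 160, so the effect cannot be sized.

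**Conclusion.** The concern holds. Taking the 30% as loss before the primary analysis, 160 enrolled gives an expected 112 analysed, 12 fewer than the 124 behind the stated 80% power. Fixed-n power at r = 0.30 and two-sided alpha 0.01 is then 0.744 to 0.747, against 0.799 in Table 3. Given expansion and a true r of 0.30, the loss is also about 5 points, from 0.844 to 0.795, so it is not shown that power would fall well below 80% in that branch. Over the whole design the loss is under 3 points at r = 0.30. The core design of 68 is not affected. If some of the 30% is follow-up loss, the shortfall is smaller by an amount the documents do not allow one to calculate.

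**What to change.** In the Sample Size Calculation section, state first whether the 30% is loss before completing the inpatient stay.

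- If it is, restate the figures: 160 enrolled is expected to give 112 completers and fixed-n power of about 75% for r = 0.30 at alpha 0.01, with 80% power for r of about 0.315.
- If it includes loss at the 6-month and 1-year visits, give the inpatient loss rate separately, with the completers and power that follow. For example, 22.5% gives 124 and 0.80; 25% gives 120 and 0.78.

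A sentence on whether re-enrolled volunteers count again toward 160 would complete the account. The cost is one or two sentences, with no change to enrolment, procedures or the core design. If the sponsor prefers to keep an expected 124 at 30% inpatient loss, the enrolment figure becomes 178, which is 18 more than now requested.
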